**Methods:** This research project will be conducted with Cleveland Clinic IRB approval and waived patients consent. (see Human Subjects section for justification). The trial will be registered at ClinicalTrials.gov (NCT04701762, date of registration January 8 2021) before enrolling any patients. A full statistical analysis plan will be developed before any data are evaluated. Reporting will be consistent with the CONSORT guidelines for pilot trials.

**Design:** The proposed quality improvement project will be conducted in an isolated set of 22 operating rooms (J operating suites) at the Cleveland Clinic Main Campus which is largely staffed by a consistent team of anesthesia attendings, nurse anesthetists and anesthesia residents and fellows with variable level of experience. Most operations in this suite are cardiac, thoracic, or vascular surgeries. Nearly all require general anesthesia, and most patients are hospitalized at least overnight.

We plan a cluster randomized multiple crossover quality improvement project. The J operating suites will be divided into 2 separate clusters consisting of 11 operating suites each (cluster 1: operating suites 60 to 70, and cluster 2: operating suites 71 to 81). Clusters were formed by physical proximity to make it as logistically feasible as possible to conduct the trial.

Randomization will consist of randomizing cluster 1 to use either videolaryngoscope or direct laryngoscope, and cluster 2 to the alternative device in one-week blocks.

Randomization, 1:1 and unstratified, will be based on computer-generated codes maintained in a web-based system that investigators will access one day before each new treatment block begins. Randomization allocations will be verbally communicated to anesthesia personnel directly and by signs prominently displayed on each anesthesia machine. In previous similar trials, compliance with designated allocations exceeded 97%.

Design notes: Cluster randomized multiple crossover cluster trials are analogous to individual patient crossover trials, except that each cluster is crossed over to the other treatment in the next period instead of individual patients crossing over. They differ from cluster randomized trials (CRT) in that each cluster receives each treatment multiple times instead of each cluster only receiving one of the interventions during the trial.

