**Interim Analyses.** We will conduct interim analyses for efficacy and futility at each 25% of the planned enrollment using a group sequential design with a gamma spending function, with gamma parameter of -4 for efficacy and -1 for futility. Assuming the alternative hypothesis is as specified below in Sample Size Considerations, there will be a cumulative 9.4% probability of crossing a stopping boundary at the first look, 40% through the 2nd look, 78 % through the 3rd look and 100% by the last. Stopping boundaries will *not* be binding – the decision to stop or continue the trial will be made by the DSMB which will consider all available information in their decision.

**Sample size considerations.** Sample size is based on the primary outcome, the number of intubation attempts (with either device). About 5,000 operations per year will be performed during the anticipated 3-year enrollment period. Based on a previous study, we expect that about 10% of patients may require more than 1 intubation attempt in the direct laryngoscopy group versus about 4% in the videolaryngoscopy group. (Direct laryngoscopy 1 attempt: 90%, 2 attempts: 4%; Videolaryngoscopy 1 attempt: 96%, 2 attempts: 4%). However, we plan the study to detect a slightly smaller effect, which also would be clinically relevant.

We assume for sample size calculation that the proportion having 1, 2, 3 or more than 3 attempts will be 0.90, 0.04, 0.03, 0.03 in the direct laryngoscopy group and 0.92, 0.04, 0.02, 0.02 with videolaryngoscopy. To detect this difference or a larger one with 90% power at the 0.05 significance level with a Mann-Whitney test we would need a total of 8,800 patients, before accounting for interim analyses or within-cluster correlations. Accounting for a small within-cluster correlation of 0.01 and even smaller within-cluster

between-period correlation of 0.009, the required total sample size  is 13,112. Further adjustment for interim analyses requires a maximum total of 14,943 patients.

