**Internal Pilot Study to Assess Sample Size Assumptions.** At the first interim analysis we will re-assess the distribution of the primary outcome in the direct laryngoscopy group only (since the prevalence can be considered a nuisance parameter analogous to standard deviation for a continuous outcome) as well as the assumed within-cluster and within-cluster between-period correlation. We will resize the study if the required N based on the revised parameter estimates is noticeably higher than originally planned for the same planned treatment effect.

**Executive summary:** Securing the airway is fundamental in surgical patients; a key component is endotracheal intubation, which is usually easy but sometime extraordinarily difficult. Direct laryngoscopy is generally used as the first-line airway device. Videolaryngoscopy improves airway visualization, but it remains unclear whether videolaryngoscopy reduces the number of intubation attempts. We therefore propose a large, robust trial powered to determine whether videolaryngoscopy reduces the need for multiple intubation attempts.

**Significance:** Most surgical patients require endotracheal intubation. Although relatively rare, difficulties during endotracheal intubation can cause substantial patient morbidity including respiratory and hemodynamic instability, hypoxemia, cardiac arrest, regurgitation, aspiration, and airway trauma. The proposed study will extend available information and will determine whether videolaryngoscopy is superior to direct laryngoscopy, and whether videolaryngoscopy should be used initially in routine practice.

**Funding:** This project is supported by an investigator-initiated grant by Verathon, Bothwell, WA.

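### The stated 13,112 (maximum 14,943) does not follow from the plan's own correlations, one-week blocks and case volume, which give about 9,135 (10,410), so stated power and stopping probabilities are too low

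*Combined protocol and SAP*

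**What the plan says.** All of this is in the combined protocol and SAP.

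- **Base size** (Sample size considerations): for 90% power at the 0.05 level, "with a Mann-Whitney test we would need a total of 8,800 patients". The assumed proportions with 1, 2, 3 and more than 3 attempts are 0.90/0.04/0.03/0.03 (direct) and 0.92/0.04/0.02/0.02 (video).
- **Clustering** (same section): "Accounting for a small within-cluster correlation of 0.01 and even smaller within-cluster" and, continuing over the page break, "between-period correlation of 0.009, the required total sample size" is given as 13,112. No cluster-period size or formula is printed; a cluster-crossover sample-size tutorial is cited.
- **Interim looks** (same section): "Further adjustment for interim analyses requires a maximum total of 14,943 patients".
- **Volume** (same section): "About 5,000 operations per year will be performed during the anticipated 3-year enrollment period".
- **Block length** (Methods, Design): there are two clusters of 11 rooms, with cluster 1 randomized to one device and "cluster 2 to the alternative device in one-week blocks".
- **Stopping probabilities** (Interim Analyses): under the sample-size alternative, "there will be a cumulative 9.4% probability of crossing a stopping boundary at the first look", then 40%, 78% and 100%.
- **Resizing** (Internal Pilot Study): both correlations are re-estimated at the first look, and "We will resize the study if the required N based on the revised parameter estimates is noticeably higher than originally planned".

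**The concern.** In a cluster-crossover design the between-period correlation offsets most of the within-period correlation. With 0.009 against 0.01 and a period of only one week, clustering should cost a few percent. The plan instead adds 49%.

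Type I error is not at risk, and the trial is over-sized rather than under-sized. What is at stake is the planning basis:

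- The stated N, power and stopping probabilities do not describe this design, and the data and safety monitoring board (DSMB) would work with the wrong expectation of early stopping.
- The resizing rule compares a new requirement with what was originally planned. If that baseline is about 44% too high, a rise in the true requirement from about 9,135 towards 13,112 would not register as an increase.
- With no cluster-period size or formula stated, the resizing cannot be reproduced. If the original step left out the 0.009, repeating it would make re-estimation of that correlation pointless.

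**Working it through.** **Inputs.** From Sample size considerations: within-period correlation ρ = 0.01, between-period correlation η = 0.009, base 8,800, about 5,000 operations a year. From Design: two clusters, one-week periods, 1:1. From Interim Analyses: four equal looks, gamma −4 (efficacy) and −1 (futility), non-binding. The plan does not state sidedness; two-sided 0.05 is assumed. Cluster-period size m is derived.

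**1. The plan's own multipliers.**
- Clustering: 13,112/8,800 = 1.4900 exactly.
- Interim looks: 14,943/13,112 = 1.1396.

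**2. Design effect from the stated inputs.**
- m = 5,000/52/2 = 48.1
- DE = 1 + (m − 1)ρ − mη = 1 + 47.1×0.01 − 48.1×0.009 = 1.0381
- 8,800 × 1.0381 = 9,135; × 1.1396 = about 10,410
- 13,112/9,135 = 1.435

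| m | DE | N | Maximum |
|---|---|---|---|
| 24 (exclusions halve volume; assumption) | 1.014 | 8,923 | 10,169 |
| 48.1 | 1.038 | 9,135 | 10,411 |
| 50 (50-week year) | 1.040 | 9,152 | 10,430 |
| 100 | 1.090 | 9,592 | 10,931 |

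**3. What gives 1.49.**
- m = 500 with both correlations: 0.99 + 0.001×500 = 1.49. That is about ten weeks of one cluster's volume.
- m = 50 with no between-period term: 1 + 49×0.01 = 1.49.
- At m = 48.1 and ρ = 0.01, it needs η = (1.4708 − 1.49)/48.1 = −0.0004.

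The documents do not show which route was taken.

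**4. The 8,800 base.**
- Mann-Whitney with ties: θ = P(direct > video) + ½P(tie) = 0.0950 + 0.4154 = 0.5104. With mean proportions p̄ = 0.91, 0.04, 0.025, 0.025, 1 − Σp̄³ = 0.2463. N = (1.96 + 1.2816)² × 4 × 0.2463/12 ÷ 0.0104² ≈ 7,977.
- Whitehead's proportional-odds formula (odds ratio 1.278): about 8,519.
- Two proportions, 10% v 8%: 8,601 uncorrected, about 8,800 with continuity correction. The plan does not say this test was used.
- On the 7,977 base: × 1.0381 = 8,281; × 1.1396 = about 9,440.

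**5. Power at 14,943.** The equivalent number of independent patients in a fixed design is 14,943/1.0381/1.1396 = 12,631.
- 8,800 base: Φ(3.2415×√(12,631/8,800) − 1.96) = Φ(1.92) = 0.973
- 7,977 base: 0.983

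**6. Stopping probabilities under the alternative.** Numerical integration with one-sided 0.025 and non-binding futility; cumulative probability of crossing either boundary:

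| Case | Look 1 | Look 2 | Look 3 | Expected N |
|---|---|---|---|---|
| Plan as stated | 9.4% | 40% | 78% | not given |
| Recomputed, 14,943 gives 90% power | 9.2% | 39.7% | 77.7% | about 10,210 |
| DE 1.038, 8,800 base | 14.6% | 56.5% | 89.7% | about 8,940 |
| DE 1.038, 7,977 base | 16.9% | 61.9% | 92.3% | about 8,550 |

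The second row reproduces the plan closely, so its probabilities presuppose that 14,943 gives exactly 90% power. Power with the looks included is 97.2% and 98.2% in the last two rows.

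**The case against.** **The plan states neither m nor a formula.** True, so 9,135 rests on a derived m and the standard crossover formula. But volume, cluster number and block length fix m closely, exclusions only lower it, and N is 8,923 to 9,592 for m between 24 and 100.

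**1.49 could be legitimate.** If each week were a fresh independent draw and the comparison ignored cluster, the 0.009 would not cancel. A simulation of that case with m = 50 gave an inflation of 1.49. This is the best defence of the figure, and the Design text leaves some room for it. It fails because the plan says the 0.009 was accounted for, and the primary model has a random effect for room within cluster. Adjusting for cluster brings the inflation back to 1.04.

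**The result is more sensitive to η than to m.** This stands as a caution. At m = 48.1, ρ = 0.01 and the 8,800 base:

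| η | N | Power at 14,943 |
|---|---|---|
| 0.007 | 9,982 | 96.0% |
| 0.005 | 10,828 | 94.6% |
| 0.003 | 11,675 | 93.0% |
| 0 | 12,945 | 90.4% |

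A cautious planner might want this reserve. It does not repair a figure stated for η = 0.009.

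**The consequences are limited.** Largely conceded. The stopping probabilities are a knock-on effect, not a second independent error. The boundaries are non-binding, and the looks already limit over-enrolment. The 8,800 label is a smaller, separate matter: the Whitehead figure is within about 3% of it, though none of the rank or ordinal calculations run gives 8,800.

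**Conclusion.** The figure is wrong as written. With the plan's correlations, block length and volume, 8,800 becomes about 9,135, not 13,112, and the maximum is about 10,410, not 14,943. At 14,943, power is about 97% (about 98% on the Mann-Whitney base) and cumulative stopping is about 15/57/90% (17/62/92%), against the stated 90% and 9.4/40/78%.

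Confidence is high that 13,112 does not follow from the stated inputs. The replacement figures rest on m of about 48, the standard crossover formula, a two-sided 0.05 level, and the assumed correlations being true. The point should be corrected, but it does not threaten the validity of the trial.

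**What to change.** 1. State the cluster-period size (about 48 per cluster-week before exclusions) and print the design-effect formula.
2. Either relabel 8,800 by the test it belongs to or replace it with the Mann-Whitney figure, and use that one base throughout.
3. Keep 14,943 as the cap. Restate its power and the matching stopping probabilities for the chosen base, preferably with a range over the between-period correlation.
4. In the Internal Pilot Study section, specify that resizing uses the crossover formula with the actual cluster-week size and both re-estimated correlations, and name the N it is compared with.
5. Leave the looks at fractions of 14,943 unless the maximum is changed before any look has been taken.

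The cost is recalculation and protocol/SAP wording, with no extra patients and no change to the cap or looks. Lowering the maximum would not be free: the Trial timeline shows enrolment from 03/29/2021, and a change after a look would alter information fractions and error spending.

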## **Chronological List of changes:**

Version 7 (march 27, 2022)

- A sensitivity analysis has been added to the statistical methods.

Version 6 (May 19, 2021)

- The ClinicalTrials.gov identifier has been added.
- The paragraph regarding video recording was updated.
- The definition of intubation attempts have been updated and specified to reflect current routine practice.

Version 5 (October 6, 2021)

- Several Co-investigators have been added.
- Video recording for teaching purposes has been added.
- The ClinicalTrials.gov identifier has been added.
- The definition of intubation attempts have been updated and specified to reflect current routine practice.

Version 4 (November 3, 2020)

- Title: "quality improvement project" was replaced by "research project"
- Several Co-investigators have been added.
- Design: we changed the isolated set of operating rooms to the J operating suites, consisting of 22 operating suites (2 are currently not in use) and used for cardiac, thoracic and vascular procedures.
- We further clarify, that we will divide the J OR's in 2 separate clusters.
- Inclusion criteria, we now enroll adults having cardiac, thoracic, or vascular surgery.
- Exclusion, we now specify, that patient requiring a double lumen tube are excluded.

- Methods: etomidate was added as an alternate induction medication
- Direct laryngoscopy. Using a Miller blade is now added as an alternative to the Macintosh blade.
- Sample size considerations: number of surgeries are adapted to about 5.000 per year and the duration of this project for up to 3 years.
- The sections on statistical analysis and *Treatment effect heterogeneity* have been updated.

#### Version 3 (May 20th, 2020)

- McGrath videolaryngoscope was replaced by GlideScope videolaryngoscope.
- We added clarification, that this project will be performed in the G operating suite area.

#### Version 2 (October 16 2019)

- Exploratory hypothesis 1 and exploratory outcome 1 was added
- The following paragraph was added “*We will also capture the level of training of the person making the first intubation attempt and the final intubation attempts (if a switch of anesthesia providers occurred).*”

**Trial timeline:**

08/20/2019	study protocol version 1 finalized
09/11/2019	initial submission of study protocol version1 submitted to IRB
12/24/2020	IRB approval granted (study protocol version 4)
01/08/2021	trial registration on www.clinicaltrials.gov
03/15/2021	Start of clinical training
03/29/2021	First patient enrolled
06/11/2021	AE reported to IRB
02/26/2022	enrollment paused due to transfer of documentation from ARKS to EPIC
03/14/2022	enrollment restarted
